---

## LIST OF ABBREVIATIONS AND DEFINITION OF TERMS

Abbreviation or special term	Explanation
12 m OS	Overall survival at 12 months after inclusion
18 m OS	Overall survival at 18 months after inclusion
6 m OS	Overall survival at 6 months after inclusion
12 m PFS	Progression-Free survival at 12 months after inclusion
6 m PFS	Progression-Free survival at 6 months after inclusion
AE	Adverse Event
AESI	Adverse Event of Special Interest
ALT	Alanine aminotransferase
AST	Aspartate aminotransferase
CI	Confidence interval
CR	Complete response
eCRF	Electronic Case report form
CTCAE	Common Terminology Criteria for Adverse Event
DoR	Duration of Response
DoR 12	Duration of Response at year
ES	Extensive-stage
ES-SCLC	Extensive-stage- Small Cell Lung Cancer
EP	Etoposide and platinum-based chemotherapy
HbsAg	Hepatitis B surface antigen
HCV	Hepatitis C virus
HIV	Human immunodeficiency virus
HPV	Human papilloma virus
HR	Hazard ratio
HRQoL	Health-related quality of life
ICF	Informed consent form
imAE	Immune-mediated adverse event
IP	Investigational product
ITT	Intent to treat
IV	Intravenous
IWRS	Interactive web response system
LSLV	last patient last visit
MOA	Mechanism of Action
NCI	National Cancer Institute

Abbreviation or special term	Explanation
NSCLC	Non-small-cell lung cancer
NTL	Non-target lesion
ORR	Objective response rate
OS	Overall survival
PD	Progressive disease
PFS	Progression-free survival
PR	Partial response
PRO	Patient-reported outcome
PRO-CTCAE	Patient-reported outcomes version of the CTCAE
PT	Preferred Term
q3w	Every 3 weeks
q4w	Every 4 weeks
QLQ-C30 v3	30-item Core Quality of Life Questionnaire, version 3
QLQ-LC13	13-item Lung Cancer Quality of Life Questionnaire
QoL	Quality of life
QTcF	QT interval corrected for heart rate using Fridericia's formula
RECIST 1.1	Response Evaluation Criteria in Solid Tumors, version 1.1
SAE	Serious adverse event
SCLC	Small Cell Lung Cancer
SD	Stable disease
SOC	System Organ Class
TL	Target lesion
TTD	Time to Treatment Discontinuation

## AMENDMENT HISTORY

Date	Brief description of change
	Not applicable

## 1. OBJECTIVES

### 1.1 Primary objective

- To describe safety profile of durvalumab in combination with platinum–etoposide as first-line treatment for patients with ES-SCLC.

### 1.2 Secondary objective

- To describe effectiveness of durvalumab in combination with platinum–etoposide as first-line treatment for patients with ES-SCLC.
- To describe the impact of durvalumab in combination with platinum–etoposide as first-line treatment for patients with ES-SCLC on patients' disease-related symptoms and Health Related Quality of Life (HRQoL) and (PROs).
- To describe health care resources use related to management of ES-SCLC patients treated with durvalumab in combination with platinum–etoposide as first-line treatment.

## 2. STUDY DESIGN AND SAMPLE SIZE

### 2.1 Overall design

[figure not shown]
This is a Phase IIIb, interventional, single arm, multicentre study to evaluate safety, effectiveness, use of resources and patient reporting outcomes in patients with ES-SCLC treated with durvalumab in combination with platinum–etoposide as first-line treatment in Spain.

This study will include approximately 85 eligible patients at participating Spanish sites.

Durvalumab will be concurrently administered with first-line chemotherapy (EP) on every 3 week (q3w) schedule for 4 to 6 cycles, and will continue to be administered as monotherapy post-chemotherapy on an every 4 week (q4w) schedule until confirmed progressive disease (PD) or unacceptable toxicity.

Prophylactic cranial irradiation (PCI) is allowed in patients showing complete or partial responses after the durvalumab + EP combination cycles, at the discretion of the investigator according to their local clinical practice.

**Figure 1. General study design**

## 2.2 Sample size

This is a safety study, and given the real-world setting, there is no formal predefined statistical hypothesis, and no formal sample size calculation will be done.

A convenience sample size of approximately 85 patients was estimated based on the expected accrual potential during 6 months in 30 sites, although the recruitment duration may be reduced or extended, until P&R approval of durvalumab in Spain for ES-SCLC based on CASPIAN results, and the number of patients recruited could be higher. A maximum of 30% of recruited patients will have ECOG performance status of 2 at baseline.

## 3. ANALYSIS SETS

### 3.1 Intention to treat (ITT) population

Intention to treat (ITT) population consisted of all enrolled patients who had received at least 1 dose of study drug (chemotherapy or Durvalumab).

### 3.2 Safety analysis set

The safety analysis set will include all included patients that received at least one dose of study treatment. Patients who were enrolled but did not subsequently go on to receive study treatment will not be included in the analysis. Patients who were enrolled but did not subsequently go on to receive study treatment will not be included in the analysis.

### 3.3 Responders analysis set

Responders analysis set will include the subset of patients, within the Safety Analysis Set who are evaluable for response analysis and who achieve an objective response.

## 4. EXPOSURE(S) AND OUTCOMES

### 4.1 Exposures

Exposure of interest: Durvalumab (MEDI4736). It will be administered in combination with first-line chemotherapy (EP), which includes SoC agents' platinum (carboplatin or cisplatin) + Etoposide, and as monotherapy after the chemotherapy phase.

#### 4.1.1 Definition of primary drug exposure

The exposure period started when the subject was administered the first cycle of study treatment (Chemotherapy plus Durvalumab).

#### 4.1.2 Overall design

Durvalumab will be concurrently administered with first-line chemotherapy (EP) on every 3-week (q3w) schedule for 4 to 6 cycles, and will continue to be administered post-chemotherapy on an every 4 week (q4w) schedule until confirmed progressive disease (PD) or unacceptable toxicity.

Durvalumab + chemotherapy combination:

- Durvalumab 1500 mg via IV infusion q3w concurrently with chemotherapy, starting on Week 0, for 4-6 cycles. If a patient 's weight falls to 30 kg or below ( $\leq 30$  kg), then the patient should receive weight-based dosing equivalent to 20 mg/kg of durvalumab after consultation between the Investigator and Study Physician, until the weight improves to above 30 kg ( $> 30$  kg), at which point the patient should start receiving the fixed dosing of durvalumab 1500 mg.
- EP: the dose of etoposide + carboplatin or cisplatin investigated will not exceed the product label dose for the given indication dose (etoposide [80 to 100 mg/m^2] via IV infusion with either carboplatin [area under the curve (AUC) 5-6] via IV infusion or cisplatin [75 to 80 mg/m^2] via IV infusion), starting on Week 0, for 4-6 cycles.

Durvalumab monotherapy:

- Durvalumab 1500 mg via IV infusion q4w, starting 3 weeks after the last infusion of the combination, until confirmed progressive disease (PD) or unacceptable toxicity. If a patient 's weight falls to 30 kg or below ( $\leq 30$  kg), then the patient should receive weight-based dosing equivalent to 20 mg/kg of durvalumab q4w after consultation between Investigator and Study Physician, until the weight improves to above 30 kg ( $> 30$  kg), at which point the patient should start receiving the fixed dosing of durvalumab 1500 mg q4w.

Unless specific treatment discontinuation criteria are met, patients will continue therapy until clinical progression or confirmed radiological progression.

#### 4.1.3 Definition of comparison drug exposure

Not applicable.

## 4.2 Outcomes

### 4.2.1 Primary outcome

**Primary objective:** To describe safety profile of durvalumab in combination with platinum–etoposide as first-line treatment for patients with ES-SCLC.

#### Endpoints analyzed:

- Incidence of grade  $\geq 3$  AEs
- Incidence of imAE.

This analysis will be performed for Safety analysis set. For all summaries of AEs, only treatment-emergent AEs will be included. Treatment-emergent AEs are defined as events present at baseline that worsen in intensity after administration of IP or events absent at baseline that emerge after administration of IP, for the period extending to 90 days after the last dose of IP.

The analysis will be performed with the information completed into the adverse event eCRF section.

Total SAEs, AESIs, AEs leading to death, and AEs leading to study drug interruption or discontinuation will be summarized by Medical Dictionary for Regulatory Activities (MedDRA) by System Organ Class (SOC) and Preferred Term (PT), causality, and maximum NCI CTCAE Grade. Deaths from all causes will be also summarized.

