Tumor assessment (RECIST 1.1) ⁱ	On-study tumor assessments will be performed following local standard practice, but at least with a maximum interval of 12 weeks, until RECIST 1.1-defined radiological progression plus an additional follow-up scan 4-8 weeks later. ^g								8.1

^a For women of childbearing potential only. A urine or serum pregnancy test is acceptable.

^b WHO/ECOG performance status should also be collected at other site visits that the patient attends, if appropriate site staff are available to collect such information. In addition, WHO/ECOG performance status should be provided when information on subsequent anticancer therapy is provided, where possible.

^c Details of any treatment for ES-SCLC (including surgery) post the last dose of IP must be recorded in the eCRF. At minimum, collect the start date and description of the subsequent anticancer therapy.

^f Patients may be contacted in the week following data cutoffs to confirm survival status. Details of any treatment for ES-SCLC (including surgery) post the last dose of IP must be recorded in the eCRF.

^g Free T3 or free T4 will only be measured if TSH is abnormal or if there is clinical suspicion of an AE related to the endocrine system.

ⁱ See Section 6.1.3, Section 8.1, and E for additional details relevant to image acquisition, RECIST 1.1 assessments, and evaluation of scans after RECIST 1.1-defined progression.

NA Not applicable; qXw Every X weeks; T3 Triiodothyronine; T4 Thyroxine; TSH Thyroid-stimulating hormone.

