9.5 Statistical analyses

Analyses will be performed by AstraZeneca or its representatives. A comprehensive statistical analysis plan will be developed and finalized within 3 months of the first enrolled patient and will describe the patient populations to be included in the analyses, and procedures for accounting for missing, unused, and spurious data.

Descriptive statistics will be used for all variables, as appropriate. Continuous variables will be summarized by the number of observations (n), mean, standard deviation, median, quartiles (Q1 and Q3), minimum, and maximum. Categorical variables will be summarized by frequency counts and percentages for each category.

For all summaries of AEs, only treatment-emergent AEs will be included. Treatment-emergent AEs are defined as events present at baseline that worsen in intensity after administration of IP or events absent at baseline that emerge after administration of IP, for the period extending to 90 days after the last dose of IP. Baseline will be the last assessment of the variable under consideration prior to the first IP dose administration.

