9.5.2 Analysis of the secondary variables

9.5.2.1 Safety variables

Adverse events

Total SAEs, AESIs, AEs leading to death, and AEs leading to study drug interruption or discontinuation will be summarized by Medical Dictionary for Regulatory Activities (MedDRA) by system organ class and preferred term, causality, and maximum NCI CTCAE Grade. Deaths from all causes will be also summarized.

Data from all cycles of will be combined in the presentation of safety data. AEs (both in terms of MedDRA preferred term and CTCAE grade) will be listed individually by patient. Any AE occurring before treatment with IP will be included in the data listings but will not be included in the summary tables of AEs. Any AE occurring within 90 days of discontinuation of IP may be included in the AE summaries, but the majority of the AE summaries will omit the AEs observed after a patient has received further therapy for cancer. Further details will be provided in the SAP. Any AE that occurs after a patient has received further therapy for cancer (following discontinuation of IP) will be flagged in the data listings.

For the change from baseline summaries for vital signs, laboratory data, ECGs, and physical examination, the baseline value will be the latest result obtained prior to the first IP dose administration.

The QTcF will be derived during creation of the reporting database using the reported ECG values (RR and QT) using the following formula:

$$QTcF = QT/RR^{(1/3)} \text{ where RR is in seconds}$$

Corrected calcium product will be derived during creation of the reporting database using the following formula:

$$\text{Corrected calcium (mmol/L)} = \text{Total calcium (mmol/L)} + ([40 - \text{Albumin (G/L)}] \times 0.02)$$

The denominator used in laboratory summaries will include only evaluable patients, ie, those who had sufficient data to have the possibility of an abnormality, for example:

- If a CTCAE criterion involves a change from baseline, evaluable patients would have both a predose and at least 1 postdose value recorded.
- If a CTCAE criterion does not consider changes from baseline, to be evaluable, the patient need only have 1 postdose value recorded.

The denominator in vital signs data should include only those patients with recorded data.

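### The SAP applies the full 90-day AE window to every AE summary and leaves out the protocol's rule for AEs after further cancer therapy, which can raise the all-cause Grade 3 or higher incidence

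*SAP*

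**What the plan says.** SAP 4.2.1 (Primary outcome) sets the rule for AE tables: "For all summaries of AEs, only treatment-emergent AEs will be included". Treatment-emergent events include "events absent at baseline that emerge after administration of IP, for the period extending to 90 days after the last dose of IP". SAP 5.1 then lists the summaries for the two primary endpoints, Grade 3 or higher AEs and imAEs, and the variables of the SAE listing. Neither section cuts, excludes or flags events by the start of subsequent anticancer therapy. The SAP mentions other anticancer therapy only in the definitions of PFS, time to treatment discontinuation and PRO deterioration.

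Protocol 9.5 has the same treatment-emergent definition, again "for the period extending to 90 days after the last dose of IP". Protocol 9.5.2.1 goes further. It first permits late events: "Any AE occurring within 90 days of discontinuation of IP may be included in the AE summaries". It then says that "the majority of the AE summaries will omit the AEs observed after a patient has received further therapy for cancer", and that AEs arising after such therapy "will be flagged in the data listings". Between these two statements it hands the matter on: "Further details will be provided in the SAP".

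The data needed for a cut exist. Protocol Table 2, footnote c, says: "At minimum, collect the start date and description of the subsequent anticancer therapy".

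**The concern.** The primary objective is the safety profile of durvalumab with platinum-etoposide as first-line treatment. Under protocol 7.1, starting another anticancer therapy ends study treatment, so the next regimen normally begins after the last dose, inside the 90 days that the AE window still covers. AEs are collected through that period (protocol 8.3.2, with visits at day 30 and months 2 and 3 in Table 2), so toxicity from the next regimen will be in the database.

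A programmer working from the SAP alone would produce no summary that leaves these events out, although the protocol says most summaries will. The Grade 3 or higher endpoint is all-cause and the study has a single arm. Nothing in the headline figure separates first-line from second-line toxicity, and no control arm shares the effect.

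**Working it through.** **Step 1: the texts side by side.**

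| Element | Protocol 9.5 | Protocol 9.5.2.1 | SAP 4.2.1 and 5.1 |
|---|---|---|---|
| Window to 90 days after last dose | Yes | Inclusion permitted | Yes |
| Omit AEs after further cancer therapy | Not stated | Yes, in most summaries | Absent |
| Flag those AEs in listings | Not stated | Yes | Absent |
| Which summaries apply the omission | Not stated | Deferred to SAP | Absent |

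The sentence limiting summaries to treatment-emergent AEs is a restriction, and it does not forbid a further one. In the protocol it stands beside the omission rule without contradiction. In the SAP it stands alone, so in practice everything inside the window is counted.

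**Step 2: the plan's own precision.** Protocol 9.2 gives exact intervals for N = 85. The Clopper-Pearson lower limit is the 2.5% quantile of Beta(x, n − x + 1), and the upper limit is the 97.5% quantile of Beta(x + 1, n − x).

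- 60%: x = 51 gives 48.8 to 70.5, half-width 10.8 points. The limits match the protocol.
- 70%: x = 60 gives 59.7 to 80.0, half-width 10.1 points. The limits match; the stated half-width is 10.0.

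The yardstick is therefore a half-width of about 10 points.

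**Step 3: direction.** Let p be the incidence of Grade 3 or higher AEs before any further therapy. Only patients with no such event up to that time can be added by counting later events. The added incidence is

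added = (1 − p) × s × q,

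where s is the share of those patients who start further therapy within 90 days of last dose, and q is the chance of a first Grade 3 or higher AE after that start and within the window. No factor can be negative, so the effect is upward or nil.

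**Step 4: size.** For p, take the 60% and 70% columns of the protocol 9.2 table; the pivotal-trial rate of Grade 3 or 4 AEs quoted in protocol 2.3.2.2, 61.5%, lies between them. The documents give neither s nor q. Assume s from 20% to 70% and q from 10% to 50%.

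| p | s | q | Added points | Patients of 85 |
|---|---|---|---|---|
| 70% | 20% | 10% | 0.30 × 0.20 × 0.10 = 0.6 | 0.5 |
| 70% | 40% | 30% | 0.30 × 0.40 × 0.30 = 3.6 | 3.1 |
| 60% | 40% | 30% | 0.40 × 0.40 × 0.30 = 4.8 | 4.1 |
| 60% | 70% | 50% | 0.40 × 0.70 × 0.50 = 14.0 | 11.9 |

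In the middle case at p = 70%, the SAP rule would report 73.6% instead of 70.0%.

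**The case against.** Five points can be made on the other side.

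- **The window is the protocol's own.** A reader might infer that the SAP widened the AE window. It did not: SAP 4.2.1 follows protocol 9.5. What is missing is the additional rule in 9.5.2.1.
- **The omission rule does not name the primary table.** It sits under secondary variables, speaks of most summaries, and allows events within 90 days to be included. Protocol 9.5.1, on the primary variables, has no cut. A reader might infer that the SAP breaches a protocol rule for the primary endpoint; the wording does not go that far. It left the choice to the SAP, and the SAP makes none. No reading of most summaries is satisfied when no summary applies the rule.
- **Causality tables help in part.** SAP 5.1 reports Grade 3 and Grade 4 AEs by causality as well as in total, so events attributed to the next regimen can be separated. The all-cause total is unchanged.
- **imAEs differ.** Their definition requires association with drug exposure and no clear alternative cause, which already screens out much second-line toxicity. Protocol 4.3.1.1 gives a durvalumab half-life of about 21 days, and protocol 8.3.2 asks for late-onset toxicity even beyond 90 days. Cutting imAEs when new therapy starts could lose true late immune events. This point stands and shapes the fix.
- **The effect may be small.** The study is descriptive, and much of the assumed range lies well inside the half-width. This is fair, but the shift has one direction and a confidence interval does not reflect it.

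**Conclusion.** The point holds as an omission with a known direction. The protocol deferred to the SAP the handling of AEs after further cancer therapy, and the SAP neither applies nor replaces the rule. Followed literally, it gives no AE summary and no listing that meets protocol 9.5.2.1, and it lets first Grade 3 or higher events after the start of second-line therapy into the all-cause primary incidence.

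That the texts are silent and that the effect cannot be downward are both certain. The size is not. The range of 0.6 to 14 points depends wholly on the assumed s and q. A reader might take from it that the primary result will be inflated by some definite amount, or might infer the overlap from the protocol's statement that almost all patients relapse. Relapse does not show that therapy starts within 90 days of the last durvalumab dose, and protocol 6.1.3 allows treatment through progression. The supported statement is that the incidence can be raised.

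The choice should be fixed in advance: the study is open-label, and SAP section 7 schedules the section 5.1 output for October 2021.

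**What to change.** In SAP 4.2.1 and 5.1:

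1. For the Grade 3 or higher incidence and the general AE summaries, end the treatment-emergent window at the earlier of 90 days after last dose or the day before the first subsequent anticancer therapy. Use the protocol's sense of further therapy, meaning therapy after discontinuation of IP, so that cranial irradiation given during study treatment does not trigger the cut.
2. Show the full 90-day count as a supportive table.
3. For imAEs, keep the full 90-day window as the main count and show the version cut at subsequent therapy as supportive.
4. Flag AEs that begin after subsequent therapy in the listings.

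The cost is SAP wording, a supportive version of each primary count and one listing variable. No new data are needed, because the therapy start date is already collected. The downside is that some true late Grade 3 or higher toxicity of the study regimen moves to the supportive count, where it remains visible.

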### 4.2.2 Secondary outcome(s)

#### 4.2.2.1 Secondary outcome 1

To describe effectiveness of durvalumab in combination with platinum–etoposide as first-line treatment for patients with ES-SCLC:

#### Endpoints analyzed:

- Progression-free survival (PFS): This analysis will be performed for the Intention-to-Treat population (ITT). PFS is defined as the time from the first date of treatment until the date of objective disease progression or death (by any cause in the absence of progression) regardless of whether the patient withdraws from IP or receives another anticancer therapy prior to progression.

**PFS (days)** = Date of event or Censor date – treatment start date +1

Patients who have not progressed or died at the time of analysis will be censored at the time of the latest date of assessment from their last evaluable assessment. However, if the patient progresses or dies after 2 or more missed visits, the patient will be censored at the time of the latest evaluable assessment prior to the 2 missed visits. If the patient has no evaluable visits or does not have baseline data, he/she will be censored at Day 1 unless he/she dies within 2 visits of baseline, in which case the date of death is the event date.

The PFS analysis will be based on the programmatically derived RECIST 1.1 using the Investigator tumor assessments. It will be analysed PFS, PFS at 6 months (6mPFS) and PFS at 12 months (12mPFS).

- Objective response rate (ORR): This outcome will be analysed for the responder's analysis set. The ORR will be based on the programmatically derived RECIST 1.1 using the investigator tumor data.
- Duration of response (DoR): This outcome will be analysed for the responder's analysis set. DoR is defined as the time from the date of first documented response per RECIST1.1 until the first date of documented progression per RECIST1.1 or death in the absence of disease progression.

DoR (days) = Date of PFS event or censoring – Date of first response +1

The end of response should coincide with the date of progression or death from any cause used for the PFS endpoint. If a patient does not progress following a response, then the patients' DoR will be censored at the PFS censoring time. DoR will not be defined for those patients who do not have a documented response. It will be analysed DoR and DoR at 1 year (DoR12)

- Overall survival (OS): This analysis will be performed for the Intention-to-Treat population (ITT). OS is defined as the time from the first date of treatment until death due to any cause.

OS (days) = Death date or Censor date - treatment start date +1

Any patient not known to have died at the time of analysis will be censored based on the last recorded date on which the patient was known to be alive. It will be analysed OS, OS at 6 months (6mOS) and OS at 12 months (12mOS) and OS at 18 months (18mOS).

- Time to Treatment Discontinuation (TTD): This analysis will be performed for the Intention-to-Treat population (ITT). TTD is defined as the time from the first date of treatment until date of discontinuation of treatment. Date of discontinuation will be the date reported in end of study form. It will be performed just on the patients that report treatment discontinuation, determined if any of the following occurs:
  - Withdrawal of consent from further treatment with IP.
  - An AE that, in the opinion of the Investigator or AstraZeneca, contraindicates further dosing.
  - Any AE that meets criteria for discontinuation as defined in the Dosing Modification and Toxicity Management Guidelines or as defined in the local prescribing information for the EP treatment.
  - Pregnancy or intent to become pregnant.
  - Non-compliance with the study protocol.
  - Initiation of alternative anticancer therapy including another investigational agent.
  - Clinical progression or confirmed radiological progression and Investigator determination that the patient is no longer benefiting from treatment with IP.

#### 4.2.2.2 Secondary outcome 2

To describe the impact of durvalumab in combination with platinum–etoposide as first-line treatment for patients with ES-SCLC on patients' disease-related symptoms and Health Related Quality of Life (HRQoL) and (PROs).

